9.2.3.2 Exposure Assessment

In this section, operational definitions for identifying exposures to vaccines and medicines should be described, including the codes to identify them in the specific data sources.

In the primary analysis, exposure should be based on <<COVID-19 vaccine>>; a secondary analysis should be conducted grouping vaccines according to platform or other characteristics (e.g., adjuvant) if needed.

Vaccine information (eg. Date of vaccination, type of vaccine platform) should be obtained from all possible sources that capture COVID-19 vaccine and influenza vaccines such as pharmacy dispensing records, general practice records, immunisation registers, vaccination records, medical records, or other secondary data sources. Depending on the data source, vaccines should be identified via nationally used product codes including batch numbers where possible.

If the vaccine is administered in multiple doses, doses should be classified separately. If the vaccine is administered as a single dose, then only the first exposure code during the study period will be considered, which assumes that the remaining codes could be recording errors and/or medication errors. In that case, a censoring at subsequent doses will be applied.

In analyses utilizing a control vaccine exposure, care should be taken that salient features of subjects and/or healthcare systems do not pose a risk for differential recording of a specific COVID-19 vaccine product and the selected control exposure. Fit for purpose assessment should be used prior to selection of a data source.

9.2.3.3 Risk & Control periods

In this section, risk and control windows should be specified for each of the events under assessment for the specific design.

The duration of the risk periods should be specific for each of the outcomes and defined to establish an accurate relationship and patterns in that relationship. Risk windows should be subdivided in smaller periods of risk to allow for investigation of changes in the estimate of risk and doses. Control periods should be chosen in a manner that there is no misclassification of exposure/event occurrence.

As general reference for risk periods and opportunity to harmonize we recommend inspection of outputs of the SPEAC project as this is creating event definition, codes, risk factors and windows for many of the AESI which will be released on the Brighton Collaboration website in the coming year (<https://brightoncollaboration.us>).

9.2.3.4 Covariate Assessment

9.2.3.4.1 Descriptive Covariates

For descriptive purposes, sex, age, country, and calendar month of vaccination should be assessed in the study population (overall and/or by index and comparison cohort/ study groups), at the start of follow-up (for cohort, SCCS, SCRI) or at the index date (case-control).

9.2.3.4.2 Confounders

Important confounders are all factors that are known risk factors for the event and are associated with the COVID-19 vaccination. Since both conditions should be fulfilled, we recommend that a list is created of all risk factors associated with the event, which are better known, and the criteria for vaccination eligibility. Accurate assessment and control for confounders is required in signal evaluation studies. The effect of confounders may be minimised by applying matching, adjustment or restrictions. Methods for retaining relevant covariates/confounders in the statistical model may be diverse including stepwise regression or 'change-in-estimate' approach (Greenland, 2016).

Risk factors for events should be obtained from the literature and classified as stable or varying within one individual over the period of the study. Factors associated with vaccination should be obtained from national authorities and may include at-risk conditions or age.

Time varying confounders that should be considered are:

- Age may act as a time-varying confounder in children, depending on the event of interest. Age may be adjusted for the self-controlled designs by dividing person-time during follow-up into pre-specified age groups (e.g., weeks or months)
- Infections (in particular respiratory)
- non-COVID-19 vaccines (in particular influenza)

Special attention should be given to bias related to healthy vaccinee bias and confounding by indication (Remschmidt, 2015).

[Investigator should add confounders relevant to specific events in this section and provide operational definitions & codes].

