9.4 Study Size

[figure not shown]
[To be completed by the study investigator(s) based on assumptions of number of cases and effect estimate size at the time of the full protocol development]

For signal evaluation studies sample size calculations should be conducted that would allow ability to detect risk with the highest precision. The sample size will be driven by the background rate of the event under evaluation and the size of the data source(s).

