9.5 Data Collection and Management

This section assumes the approach of a distributed network of DAPs who agree to use a common protocol, common data model and common analytics. We recommend to prepare for a model where original data remain local, and are transformed in a common data model that will allow for study specific structural and semantic harmonization (model C, **Figure 6**) (Gini et al, 2020).

Figure 6. Options for multi-database studies in Europe

[If other models are used this section should be adapted]

In short, model C requires that each data access provider will extract the data required for the study and transform their local patient level data into a common data model (CDM). An example of a widely used common data model in Europe (currently 24 DAPs) is the ConcePTION CDM, which is publicly available². Extract, transform and load (ETL) design and instructions are available, as well as tools to check the quality of the data for the AESI listed above as these are also utilized for the ACCESS background rate protocol.

A common program to run quality checks, data transformation, and analysis should be prepared and verified and be sent to all DAPs. Aggregate results and summary estimates resulting from the programs should be returned to a single coordinating centre for pooled meta-analysis and reporting.

Routine procedures should include checking electronic files, maintaining security and data confidentiality, following analysis plans, and performing quality-control checks of all programs. Each partner should maintain any patient-identifying information securely on site according to internal standard operating procedures or guidance documents.

² <https://www.imi-conception.eu/wp-content/uploads/2020/10/ConcePTION-D7.5-Report-on-existing-common-data-models-and-proposals-for-ConcePTION.pdf>

Security processes should be in place to ensure the safety of all systems and data. Every effort should be made to ensure that data are kept secure so that they cannot be accessed by anyone except the study team.

Appropriate data storage and archiving procedures should be followed by each DAP and the coordinating organization, with periodic backups. Standard procedures should be in place at each research centre to restore files in the event of a hardware or software failure.

[Investigators should modify this section as needed for the specific study; if specific procedures of the identified research partners are known, they can be included here]

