9.6.3 Data Integration

Results should be presented separately for each data source and pooled across data sources. The method for pooling of results will depend on the data-sharing policies of each of the participating data sources (see **Section 9.4**). We recommend for multi-site studies that aggregated data is shared and pooled. (Yoshida, 2018; Li, 2018; Shu, 2019).

If database access providers do not allow the necessary aggregate data to be shared, then data analysis will be performed by DAPs at their sites. Counts and coefficients would be shared with the study coordinating centre, and overall results would be summarised using meta-analytic techniques, such hybrid approaches were utilized previously to analyse narcolepsy data for the pandemic vaccine (Weibel, 2018).

Meta-analysis will be conducted using standard methods: heterogeneity should be tested and Forest plots be provided. Because of the size of data-sources we recommend random effect models (DerSimonian and Laird, 1986).

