9.8 Limitations of the Research Methods

The different proposed study designs are subject to limitations due to both the study design and secondary use of health care data.

Data-related limitations include dependency on the accuracy of codes and algorithms to identify outcomes, and the opportunity to confirm events. Misclassification of events (both diagnosis and date of onset) may be minimised by conducting validation and assessing certainty by using BC event definitions. However, the

use of medical records and other secondary data sources for validation purposes may limit the ability to apply Brighton Collaboration criteria and other standardised case definitions to confirm outcomes and to identify true onset of the outcomes.

Exposure ascertainment may be based on pharmacy dispensing records, general practice records, immunization registers, medical records, vaccination cards, or other data sources. The ability to identify specific COVID-19 vaccines and dates of vaccination are currently unknown as it is not clear how the vaccines will be rolled out and what level of detail will be recorded. ACCESS promotes the recording and identification of vaccine brands and batch numbers/ lot numbers. It is likely that subjects vaccinated outside of the healthcare system may not have a record of their vaccination. If brands cannot be distinguished, there may be misclassification of exposure which is of essence due to the differences in platforms and adjuvants. Inability to distinguish lots would misclassify exposure and would be important if any safety signal is related to vaccine production.

Cohort studies are usually less suitable to assess rare events. However, the use of secondary data collection allows for the inclusion of large sample size and increases the statistical power for small risk characterization. A main limitation relates to risk of immortal time bias when inclusion is based on the presence of a certain period of follow-up.

Unvaccinated subjects may become exposed to COVID-19 vaccine at any time over the course of study, censoring in the follow-up time may create an imbalance in the observation periods between vaccinated and unvaccinated groups, which is not random. Another important limitation relates to residual confounding due to unmeasured confounders as it is unlikely that the data sources will comprise information on all potential confounders.

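### The only methods named for keeping confounders in the model, stepwise regression and change-in-estimate, let the outcome data remove factors that the protocol asks to have listed and controlled

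*Protocol*

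**What the plan says.** Section 9.2.3.4.2 starts from subject knowledge. It defines a confounder by two conditions, being a risk factor for the event and being associated with vaccination. To support this, "we recommend that a list is created of all risk factors associated with the event", together with the criteria for vaccine eligibility. It adds: "Accurate assessment and control for confounders is required in signal evaluation studies". Three routes are offered: "The effect of confounders may be minimised by applying matching, adjustment or restrictions".

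For the adjustment route, the next sentence reads "Methods for retaining relevant covariates/confounders in the statistical model may be diverse including stepwise regression or" the change-in-estimate approach. No other retention method is named. The protocol gives no threshold, no set of factors that must stay in, and no covariate set common to all databases.

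Three other places bear on the point:

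- Section 9.5 assumes "a distributed network of DAPs who agree to use a common protocol, common data model and common analytics".
- Section 9.6.3 says: "Results should be presented separately for each data source and pooled across data sources". It prefers pooling shared aggregate data. Where these cannot be shared, the data access providers analyse locally and send coefficients for random-effects meta-analysis.
- Section 9.8 puts rare events in scope ("Cohort studies are usually less suitable to assess rare events") and relies on large secondary data to compensate.

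**The concern.** The list and the retention methods pull in different directions. A factor enters the list because it is already believed to confound. Whether it confounds does not depend on its p-value in one database, nor on whether removing it moves one noisy estimate by a set amount. When events are few, a real confounder will often miss significance and be dropped, and its confounding returns to the estimate. Section 9.8 attributes residual confounding to unmeasured factors. Selection adds confounding from measured ones, which is avoidable.

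The primary objective is to detect an increased risk, so a modest bias matters. If people at higher risk of the event are vaccinated first, the bias points towards false harm. If healthier people are vaccinated first, the same mechanism with the sign reversed would mask harm. Section 9.2.3.4.2 itself warns of both patterns. Because this is a template whose wording may be kept unchanged (section 8), the sentence can pass into many studies.

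**Working it through.** **Inputs.** The protocol states no event count, significance level or retention threshold (section 9.4 leaves study size to the investigator), so there is no figure to reproduce. Everything below is assumed: 30 to 1000 events per database, binary confounders, stepwise as backward elimination at two-sided p<0.05, change-in-estimate at 10%, no matching, and a true vaccine rate ratio (RR) of 1.0.

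**Step 1: chance that a true confounder survives p<0.05.** With D events, confounder prevalence q = 0.30 and confounder rate ratio RRc:

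P(retained) ≈ Φ( ln(RRc) × √(D·q·(1−q)) − 1.96 )

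For RRc = 1.5 and D = 60: 0.405 × √(60 × 0.21) − 1.96 = 0.405 × 3.55 − 1.96 = −0.52, which gives 30%.

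**Step 2: Poisson simulation with six confounders**, each with RRc = 1.5 and weakly tied to vaccination.

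| Events | P(retained), RRc 1.5 | P(retained), RRc 2.0 | Stepwise: share dropped | Stepwise: mean RR | Change-in-estimate: share dropped |
|---|---|---|---|---|---|
| 30 | 17% | 41% | 82% | 1.14 | 65% |
| 60 | 30% | 69% | 67% | 1.10 | 59% |
| 120 | 53% | 94% | 43% | 1.05 | 54% |
| 300 | 90% | ~100% | 9% | 1.01 | 47% |
| 1000 | ~100% | ~100% | 0% | 1.00 | 41% |

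The model with all six confounders gave mean RR 1.00 to 1.02. Change-in-estimate stayed near RR 1.08 at every size. Its coverage fell to 90% at 300 events and 75% at 1000, because the bias stays while the interval shrinks. The reason is simple: the crude RR was about 1.24, so each confounder contributes about 1.24^(1/6) = 1.036. No single one moves the estimate by 10%, and the rule tolerates shifts of that order whatever the event count.

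**Step 3: eight confounders in the same direction** (log-odds 0.5 with vaccination, log-rate 0.4 with the event). Three sets of runs of this kind, at about 36, 72 and 145 events, gave these mean RRs under backward selection:

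- 300 runs: 1.23, 1.13, 1.09, with false harm 7–8%
- 500 runs: 1.22, 1.16, 1.07
- 200 runs: 1.19, 1.14, 1.11, with false harm 9–10%

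The full list gave RR 0.99 to 1.03 and false harm 1–4%. The Monte Carlo standard error of a 7.5% rate in 300 runs is √(0.075 × 0.925 / 300) = 1.5 points. For 9.5% in 200 runs it is √(0.095 × 0.905 / 200) = 2.1 points. The excess over 2.5% is therefore not simulation noise. Change-in-estimate gave RR 1.06 to 1.10 and false harm 4–7%.

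Two conditions remove the stepwise bias:

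- At about 690 events, backward selection gave RR 1.00 and 2.4% false harm. At about 630 events it was again harmless, while change-in-estimate still gave RR 1.08 with 83% coverage.
- With half the confounders reversed in direction, RR was 0.99 to 1.01, coverage 93–95% and false harm 2–4%.

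**Step 4: interval width.** Under stepwise selection with confounders weakly tied to vaccination (odds ratio 1.5), the ratio of model to empirical standard error was 0.94 to 0.99 and coverage 93–96%, a small loss. With one confounder strongly tied to vaccination (odds ratio 6) and 50 to 200 events, the ratio was 0.86 to 0.96 and per-database coverage 87–94%.

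**Step 5: fitting per database.** Eight databases with identical populations selected on average 5.8 different stepwise models at 30 events, 7.5 at 120, 3.9 at 300 and 1.0 at 1000. Change-in-estimate selected about 7.2 to 7.5. In the odds-ratio-6 case, DerSimonian–Laird pooling did not remove the bias: with RRc = 1.5 and 50 events, RR was 1.18 both per database and pooled, while coverage went from 89% to 72%. Across these settings pooled coverage was 64–94%, against 96–98% for the full model. A standard-error ratio of 0.874 means 1/0.874² = 1.31, so estimates vary 31% more than their reported variances imply, which a heterogeneity test would partly read as a difference between databases.

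**The case against.** The strongest reply is that the sentence prescribes nothing. It gives two examples in a template that investigators must adapt, and the final retention rule commonly sits in a statistical analysis plan, which is not at hand. A reader might infer that the primary model will be chosen stepwise; the protocol does not say so. This stands, and it makes the harm conditional. It does not dispose of the point, because the complaint is not about missing detail: a later plan using either method would comply with the protocol.

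Scope is also narrower than it may look. The cohort comparator is matched by frequency or propensity score (9.1.1), case-control sets are matched on at least age, sex, database and calendar time (9.1.2), and self-controlled designs remove fixed confounders (9.1.3). The simulations have no matching, so they describe only the factors left to regression. This stands too.

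A reader might infer that selection contradicts section 9.5. It does not: one program applying one rule everywhere is still common analytics, and different selected models are a possible result where models are fitted per database, as in the fallback of 9.6.3. A reader might also take narrow intervals as the main harm. Step 4 shows that effect is usually small; the bias matters more, and the low pooled coverage needs a confounder very strongly tied to vaccination and left open to selection.

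Finally, an instruction to keep every listed factor in every database would be too rigid. Section 9.6.5 expects some time-varying confounders to be missing in some sources, and the list also holds eligibility criteria that may not be confounders. The fix has to allow for both.

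**Conclusion.** The point holds as a fault in the guidance, not as a proven error in any analysis. The section requires confounder control, asks for a list, and then names only methods that let the outcome data undo it. For factors left to regression adjustment, with confounders pushing the same way and roughly 30 to 150 events per database, stepwise selection at p<0.05 biases the rate ratio by about 5 to 20% (1.05 to 1.23 across the runs). False harm findings rise to about 7 to 10%, against a nominal 2.5%, in the eight-confounder runs. Stepwise does little harm at several hundred events or when directions cancel. A 10% change-in-estimate rule can leave about 8% bias even with many events. Differing models across databases are a risk that adds heterogeneity. All sizes depend on the assumed event counts, confounder strengths and thresholds, none of which the protocol gives. The sentence should be changed because a better rule is available at little cost.

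**What to change.** Replace the sentence on retention methods in section 9.2.3.4.2 with:

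> For each event, the factors on the list judged to be confounders (risk factors for the event that are also associated with vaccination) are pre-specified and retained in the primary model in every database that records them, regardless of significance; where events are few they are summarised in a propensity score fitted without the outcome. Data-driven selection (stepwise or change-in-estimate) is used only as a sensitivity analysis, run identically in all databases. Confounders not available in a data source are handled as in 9.6.5.

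Section 9.6.5 speaks only of time-varying confounders, so its wording should be widened to cover any listed confounder that a source lacks.

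The cost is small. The list is already recommended and propensity scores already appear in 9.1.1. The extra work is to mark which listed factors meet both conditions. The statistical price is intervals about 2 to 4% wider when events are few.

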9.1.1 Cohort

Retrospective (multi)-database cohort study where index <<COVID-19 vaccinated>> subjects and reference (subjects not vaccinated with << COVID-19 vaccine>>: reference cohort) are compared for occurrence of << event>>.

The comparison cohort will be matched using as example frequency matching or propensity score matching for important covariates such as age, sex and comorbidities (including COVID-19 infection prior to reference date) and markers of health care utilization (Austin, 2011). The comparison cohort could be the following:

- A concurrent comparison cohort including subjects not vaccinated with <<COVID-19 vaccine>> at the time of study start, identified at the same date (+/- 7 days – eg. anchored on a healthcare visit or pharmacy dispensing) of the exposure date (1st vaccine dose in case of multi-dose vaccine) of the matched vaccinated subjects. This calendar date time matching will allow to control for the variation in the SARS-CoV2 circulation and will minimize the risk of immortal time bias given that the time period before vaccination is immortal. To test for the presence and magnitude of immortal time, the time

difference between cohort entry and the date of start of vaccine distribution should be calculated for each cohort member and the frequency distribution of immortal time compared between the vaccinated and unvaccinated cohorts.

- If <<COVID-19 vaccine>> is distributed concurrently with the seasonal influenza vaccine, persons receiving both <<COVID-19 vaccine>> and the seasonal influenza vaccine could be compared with those receiving the influenza vaccine alone.
- A comparison cohort including subjects vaccinated with alternative <<COVID-19 vaccine>> in the same week as the matched index subjects. This time matching will allow to control for the variation in the SARS-CoV2 circulation.
- In the instance where the risk period of <<event>> is well known, the comparison cohort may be the same persons as the index cohort, with the comparison person time chosen after the ending of the risk window. Time trends in events cannot be controlled for in this manner.

[figure not shown]
The incidence rate ratio of the <<event>> is calculated comparing the incidence rate in index with that in the comparison cohort. The required follow-up time will depend on the event under evaluation, this follow-up time should take into account the vaccination schedule (**Figure 1**).

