9.1.2 Matched case-control

[figure not shown]
Retrospective (multi)-database case-control study where COVID-19 vaccination status is compared between cases (subjects who experienced << event>>) and controls (subjects who did not experience << event>>) in a specific time window.

Cases and controls should be matched on strong risk factors for the event and we recommend at least: age (year of birth), sex, and database (in case of multiple databases used) as well as calendar time. Controls should arise from a population where prior probability of exposure is the same as for the cases and be eligible to become and observed as a case if they develop the event of interest at a later date. As such persons may serve as control prior to becoming a case and may serve as a control for multiple cases (Richardson, 2004).

Index date for cases should be the disease date (preferably date of onset or first symptoms, otherwise diagnosis), the index date for the controls should be the index date of the corresponding cases. The calendar time matching, controls for confounding due to time related issues (e.g. circulation of SARS-Cov-2). Controls should be sampled using incidence density sampling (Lubin, 1984). For each subject in the database the start and end of follow-up is calculated, exclusion criteria are applied to all subjects and upon occurrence of an exclusion criterion, the follow-up time is censored. For each case, controls subjects who are actively registered in the data source at the index date of the case can be sampled or all eligible controls may be used (recommended if stratified analysis are conducted) (**Figure 2**).

In a case-control study, the aim is to compare the exposure during a specific time window between cases and controls. The time window prior to index date should be disease-specific plus the latency time period for the event under evaluation (e.g. for long latency events). For events with long latency, the risk window should be shortened or divided in small intervals to be able to assess the pattern of risk across different time windows. General recommendations are to have a time window of at least 2 months for events with short latency, and 3 years for events with long latency.

Figure 2. Case-control design

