9.7 Quality Control

Standard operating procedures or internal process guidance at each research centre should be adhered to for the conduct of the study. These procedures should include internal quality audits, rules for secure and confidential data storage, methods to maintain and archive project documents, quality-control procedures for programming, and standards for writing analysis plans.

This section should describe the study-specific process for programming quality control (e.g., independent programming and/or review of summary output and programming logs by a second programmer), and procedures for data storage, archiving, and backup at each study centre. Also described should be processes for review and quality control of study documentation and reporting of pooled results across research centres.

Note to future investigators: The pandemic has led to changes in healthcare utilization and provision which are likely to extend into the vaccine roll-out period. This may be reflected in observational data as an excess of code counts for a subset of AEsI and/or their proxies in the pandemic period, or as a deficit for others. In order to understand these changes to the data available for analysis, it is recommended that counts and rates of both individual codes utilized in any event case-identification algorithm as well as the set(s) of codes chosen to identify each event be described over time both within and between databases, taking into account the type of database and the type of healthcare encounters typically captured (general practice vs. hospitalization). These counts and rates should be compared graphically in order to aid interpretation of study results.

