Event temporarily decreases or increases likelihood of vaccination	✓	✓	✓	✓	✓
Event is a (permanent) contraindication to vaccination	O ^b	O ^b	O ^b	O ^b	✓
Event censors the period of observation for exposure (e.g., death or an outcome that increases the probability of death such as myocardial infarction)	✓	✓	X	X	✓
Event is independently recurrent	✓	✓	✓	✓	✓
Event is non-recurrent but rare	✓	✓	✓	✓	✓
Event is recurrent, and recurrent events are not independent (e.g., stroke)	✓	✓	O ^c	X	O
Temporal trends in vaccination					
Temporal trends in vaccination are not present during the study period	✓	✓	✓	✓	✓
Temporal trends in vaccination are present during the study period	✓	✓	✓	✓	O

Checkmark indicates design is suitable; X indicates not suitable; O indicates that the study design is possible under certain circumstances.

^a Suitable if prodromal symptoms before diagnosis of the outcome do not cause or prevent vaccination, either temporarily or permanently. To address this potential source of bias, every effort should be made to identify the onset of symptoms from the available data such as medical records, rather than relying on the date of diagnosis.

^b Suitable if the vaccine is given in a single dose. If the vaccine is given in multiple doses, the design is not suitable unless special analytic techniques are applied to handle censored, perturbed, or curtailed post-event exposures.

^c Suitable if appropriate adaptations to the self-controlled case series are applied (Farrington, 2010)

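### The time-varying confounder list omits calendar time, so SCCS and SCRI estimates can absorb background trends in event incidence that the protocol itself expects

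*Protocol*

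**What the plan says.** Section 9.2.3.4.2 introduces its list with "Time varying confounders that should be considered are". Three items follow: age in children, infections (chiefly respiratory) and non-COVID-19 vaccines (chiefly influenza). The only person-time banding described for the self-controlled designs is by age. The section closes with an instruction to the user: "Investigator should add confounders relevant to specific events in this section and provide operational definitions & codes".

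Elsewhere the protocol expects time trends and deals with them design by design:

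- **Cohort (9.1.1):** comparators are matched on calendar date or week, to control for variation in virus circulation. For comparison time in the same vaccinated persons after the risk window, the protocol warns: "Time trends in events cannot be controlled for in this manner".
- **Case-control (9.1.2):** "The calendar time matching, controls for confounding due to time related issues", with virus circulation as the example.
- **Case-crossover (9.1.4):** a case-time-control adaptation is required because of trends in vaccination.
- **SCCS and SCRI (9.1.3):** risk and control windows are defined, and control of fixed confounders is claimed. Table 4 names conditional Poisson regression. No calendar term appears.
- **Quality control (9.7):** "The pandemic has led to changes in healthcare utilization and provision which are likely to extend into the vaccine roll-out period". The response is to describe code counts and rates over time and compare them graphically.
- **Annex 3:** the row "Temporal trends in vaccination are present during the study period" rates SCCS and SCRI as suitable without condition. There is no row for trends in event incidence.

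Calendar month of vaccination and of exposure appears only descriptively (9.2.3.4.1 and 9.6.1).

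**The concern.** A self-controlled design removes what is constant within a person. A background event rate that moves with the epidemic, the season or access to care is not constant. Unless the model accounts for it, it enters the IRR whenever risk time and control time fall at different calendar times.

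In the SCRI of section 9.1.3.2 the control window always follows the risk window, so the bias has a direction: a falling background rate looks like vaccine harm and a rising one like protection. That layout is the one for which section 9.1.1 gives its warning, but the warning is not repeated for SCRI in 9.1.3.2 or in the limitations (9.8). In SCCS the bias depends on when vaccination clusters relative to the trend.

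Table 2 marks SCCS and SCRI as usable for most of the non-pregnancy events, some subject to a known risk period. A study team that follows the listed confounders and the Annex 3 ratings could therefore report a spurious signal, or miss a real one, in much of the template's scope.

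**Working it through.** The protocol leaves study size to the investigator and gives no event rate or trend, so there is no stated figure to reproduce. The trend sizes and roll-out shapes below are assumptions. The true IRR is 1 throughout.

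**1. SCRI, bias by window length.** Inputs: adjacent equal windows with control after risk (9.1.3.2); the 42/42-day example (note to Figure 4); an assumed log-linear change of proportion *c* per 42 days. For windows of *w* days:

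null IRR = (1 + c)^(−w/42)

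| Change per 42 days | w = 42 | w = 14 | w = 7 | w = 2 |
|---|---|---|---|---|
| −20% | 1/0.8 = 1.25 | 1.08 | 1.04 | 1.01 |
| −30% | 1/0.7 = 1.43 | 1.13 | 1.06 | 1.02 |
| +50% | 1/1.5 = 0.67 | 0.87 | 0.94 | 0.98 |

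The 2-day column is relevant because section 9.1.1 uses 48 hours for anaphylaxis.

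**2. SCRI, false-positive rate at 42/42 days.** With 200 cases (assumed) and a two-sided 5% test of p = 0.5 (normal approximation), the upper rejection limit is 0.5 + 1.96 × √(0.25/200) = 0.569.

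- 20% fall: p = 1.25/2.25 = 0.556, SE 0.0351, z = (0.569 − 0.556)/0.0351 ≈ 0.39; rejection in about 35% of studies.
- 30% fall: p = 1.43/2.43 = 0.588, SE 0.0348, z = (0.569 − 0.588)/0.0348 ≈ −0.54; rejection in about 71%.

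**3. SCCS, bias.** Two assumed settings:

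- 180 days of observation, a linear change in event rate of −50% to +100%, and early or late vaccination (mean day 50 or 110): null IRR 0.83 to 1.19.
- 365 days, a 42-day risk window, a sinusoidal rate, and vaccination dates with SD 30 days. For peak-to-trough ratios of 1.25, 1.5, 2 and 3, the null IRR is 1.11, 1.21, 1.37 and 1.60 if vaccination clusters near the peak, and 0.90, 0.81, 0.70 and 0.55 near the trough.

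**4. Does calendar adjustment remove the bias?** In a small simulation of a 42/42-day SCRI (600 cases, 25 replicates per scenario, vaccination-date SD 15 or 35 days), crude IRRs were 1.24 to 1.26 for the 20% fall and 1.45 to 1.47 for the 30% fall. With 14-day calendar bands they were 1.00 to 1.05 and 1.03 to 1.07.

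**5. What it costs.** From the conditional Poisson information at IRR = 1, the variance of log IRR is multiplied by 1/(1 − R²), where R² is the share of within-person variation in the risk indicator explained by the calendar bands. Roll-out dates are assumed normal.

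| Design | Bands | Roll-out SD | Variance multiplier |
|---|---|---|---|
| SCRI 42/42, vaccinated only | 2 weeks | 60 down to 7 days | 3.7 to 5.4 |
| SCRI 42/42, vaccinated only | 4 weeks | 60 down to 7 days | 3.1 to about 4 |
| SCCS, 180 days, vaccinated only | 2 to 4 weeks | 30 to 45 days | about 1.1 to 1.4 |
| SCCS, 180 days, plus as many unvaccinated cases | 2 to 4 weeks | 15 to 45 days | about 1.04 to 1.3 |

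In SCCS the cost becomes large only when roll-out is very concentrated. In the vaccinated-only SCRI it is large at every spread examined.

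**The case against.** The strongest reply is that this is a template with an open list. Users are told to list all risk factors for the event, classify them as stable or varying within a person, and add confounders. Nothing forbids calendar adjustment, and the coding of bands can be left to an analysis plan. Part of this stands: the exact banding need not be fixed here. But the closing instruction asks for event-specific confounders, whereas calendar time is common to all events. The template also already deals with time trends in its other designs.

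Three stronger readings are tempting, and the documents do not support them.

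- A reader might infer that SCCS and SCRI have no protection at all. Recorded infections are on the list and partly stand in for virus circulation. Section 9.6.5 adds sensitivity analyses on windows and time-varying confounders, and 9.7 asks for rates as well as counts over time. None of these adjusts for unrecorded infection, care-seeking, coding or season, but they are not nothing.
- A reader might infer that every self-controlled estimate will be biased. Bias needs a trend in the event rate and, in SCCS, risk time unevenly spread over calendar time. It shrinks quickly with short windows.
- A reader might take the 9.1.1 sentence "Time trends in events cannot be controlled for in this manner" as an error. It is an honest statement of what that choice of comparison time achieves. The precision results for SCRI partly bear it out.

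The Annex 3 row "Temporal trends in vaccination are present during the study period" is not shown to be wrong either. It concerns vaccination trends and does not address trends in event incidence.

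**Conclusion.** The concern holds as an omission that can bias results. Calendar time or season is missing from the time-varying confounders, and no other section supplies it for SCCS or SCRI, although the protocol expects the trends and handles time in its other designs. The case-crossover remedy addresses trends in exposure; the matching in the cohort and case-control designs addresses calendar time directly.

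The size depends on window length and on trends that the documents do not quantify. Under an assumed fall of 20% to 30% per six weeks, the 42/42-day SCRI has a null IRR of 1.25 to 1.43. The same trend matters little for windows of a few days. For SCCS the null IRR runs from 0.83 to 1.19 in the 180-day setting, and from 0.55 to 1.60 under the most marked seasonal pattern assumed. The case for within-model calendar bands is strong in SCCS. In SCRI it is a trade-off between bias and precision.

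**What to change.** 1. **Section 9.2.3.4.2:** add calendar time/season to the time-varying list for the self-controlled designs.
2. **SCCS (9.1.3.1, Tables 3 and 4):** include pre-specified calendar bands, for example of 2 to 4 weeks and per data source, in the conditional Poisson model. Allow unvaccinated cases to help estimate them; 9.1.3.1 and Table 3 currently restrict SCCS to vaccinated cases. The precision cost is small unless roll-out is very concentrated.
3. **SCRI (9.1.3.2, 9.6.5):** do not mandate within-model bands, since a 3- to 5-fold rise in variance means needing about three to five times the cases. When windows are long, require either a calendar-time-adjusted sensitivity analysis or an adjustment using an externally estimated trend, for example from background rates or unvaccinated cases.
4. **Section 9.8 and Annex 3:** state that trends in event incidence make SCCS and SCRI conditional on such adjustment. In Annex 3 this could be a new row beside the one on vaccination trends.

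The 9.1.1 sentence on time trends can stay as it is. The changes are to template wording and analysis specification. The one added data need is unvaccinated cases or background rates over calendar time; section 9.5 already refers to the ACCESS background-rate work.
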